4. SELECTION AND ENROLLMENT OF PARTICIPANTS

Participants will be recruited through referrals from staff at the University Pain Center, Midwest Orthopedic Clinic and Neurosurgery Clinic at Rush University, the Vanderbilt University Medical Center Interventional Pain Clinic, and the Osher Center for Integrative Medicine at Vanderbilt. Additionally, we will recruit in the community via flyers posted at community physician waiting rooms and other public sites, local newspaper ads, Facebook ads, and online patient recruitment systems (Vanderbilt e-mail recruitment system, My Research at Vanderbilt, Research Match). My Research at Vanderbilt is an informatics-based recruitment tool that uses Vanderbilt University Medical Center EMR data to match individuals expressing interest in research participation with studies which may be of interest to them. Research Match (ResearchMatch.org) is a national electronic, web-based recruitment tool that was created through the Clinical & Translational Science Awards Consortium in 2009 and is maintained at Vanderbilt University as an IRB-approved data repository. We have used all of these recruitment approaches in our prior work with a high degree of success. In addition, potentially qualifying individuals who have participated in past studies in our labs who have expressed an interest in writing to be contacted for future research may be contacted as well.

Participants will: 1) have significant daily chronic pain intensity (≥ 4 on a 10-point scale) and interference in performing daily activities due to pain (≥ 3 on a 10-point scale) for at least 3 months; and 2) be between age 18-75 years inclusive. Participants will not be using opioid analgesics or Kratom on a daily basis or within 3 days of each laboratory session (confirmed via urine drug screen).

Participants will not: 1) meet criteria for past or present psychotic or bipolar disorders; 2) be unable to understand English well enough to complete questionnaires or participate in therapy; 3) have pain due to malignant conditions, rheumatoid arthritis, frequent migraines or tension headaches, complex regional pain syndrome, or fibromyalgia syndrome; 4) have had lumbar surgery within past 6 months; 5) be pregnant; 6) have signs of nerve root compression (i.e., positive straight-leg raise $<45^\circ$); 7) have liver disease such as hepatitis or cirrhosis; 8) have osteoporosis; 9) an active suicidal ideation with intent; 10) have opioid-dependency or daily use of Kratom; 11) have trouble holding their breath for 15 seconds; 12) have acute trauma to spine; 13) have long term use of corticosteroids; 14) have a spinal cord stimulator, an IT pump, or a similar device; 15) history of spinal fusion surgery; 16) arthritis of the hand, carpal tunnel syndrome, or any neuropathic pain diagnoses affecting the upper limbs; or 17) a BMI of ≥ 40 .

4.1 Inclusion Criteria

Inclusion criteria are: 1) musculoskeletal pain of the lower back and/or leg pain stemming from degenerative disk disease, spinal stenosis, or disk herniation (radiculopathy subcategory), or muscular or ligamentous strain (chronic myofascial pain subcategory); 2) able to verify chronic pain diagnosis via written confirmation

from a physician; 3) significant daily chronic pain intensity (≥ 4 on a 10-point scale) and interference in performing daily activities due to pain (≥ 3 on a 10-point scale) for at least 3 months; 4) age 18-75 years, and 5) not using opioid analgesics or Kratom on a daily basis or within 3 days of each laboratory session (confirmed via urine drug screen).

Eligibility will be determined by MD review of medical records and RA administration of relevant items from the Mood Disorder, Psychotic Screening and Substance Use Disorders Modules of the Structured Clinical Interview for DSM-V Axis I Disorders - Non-Patient Edition (SCID-V/NP;77). General health will be assessed as will circumstances of the onset of low back pain, the sequence of events in terms of medical intervention to date, exacerbating/ameliorating factors, medications used currently and in the past, previous diagnostic modalities employed, and previous medical interventions and their impact.

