4.2 Exclusion Criteria

Exclusion criteria are: 1) meet criteria for past or present psychotic or bipolar disorders; 2) inability to understand English well enough to complete questionnaires or participate in therapy; 3) pain due to malignant conditions, rheumatoid arthritis, frequent migraines or tension headaches, complex regional pain syndrome, or fibromyalgia syndrome; 4) lumbar surgery within past 6 mos; 5) pregnant; 6) signs of nerve root compression (i.e., positive straight-leg raise $<45^\circ$); 7) have liver disease such as hepatitis or cirrhosis; 8) have osteoporosis; 9) have an active suicidal ideation with intent; 10) opioid-dependency or daily use of Kratom; 11) inability to hold breath for 15 seconds; 12) acute trauma to spine; 13) long term use of corticosteroids; 14) have a spinal cord stimulator, an IT pump, or a similar device; 15) history of spinal fusion surgery; 16) arthritis of the hand, carpal tunnel syndrome, or any neuropathic pain diagnoses affecting the upper limbs; or 17) a BMI of ≥ 40 .

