5. STUDY INTERVENTIONS

5.1 Interventions, Administration, and Duration

Drug Manipulation

Although not actually an intervention, we will administer naloxone during half of the pain induction sessions in order to quantify endogenous opioid (EO) function. We will use a placebo-controlled opioid blockade procedure to assess treatment-induced changes in EO function, by comparing pain responses under placebo to pain responses after opioid blockade with naloxone at pre- and post-treatment. Naloxone is an opioid antagonist with a brief half-life (1.1 hours; 78). We will use a weight-

adjusted dose of 0.11 mg/kg with a maximum dose of 8mg (8mg dose for a 160 lb. individual, consistent with our past work 69-71). As in our past studies, naloxone in 20 ml normal saline will be infused over a 10-minute period through an intravenous cannula placed in the non-dominant arm. At this dosage, naloxone provides effective blockade of all three major opioid receptor subtypes (79). Naloxone is FDA approved, and appears to have no clinical effects in non-opiate dependent individuals. Thus, participants using opioid analgesics on a daily basis or within 3 days of each laboratory session (confirmed via urine drug screen) and/or experiences withdrawal symptoms with the initial naloxone administration, will be excluded. It has been used safely at similar dosages in previous studies, including our studies in CLBP samples (68-72). Peak naloxone activity will be achieved approximately 10 minutes following completion of the infusion. A second dose of naloxone (0.055 mg/kg with a maximum dose of 4mg; 4mg for a 160 lb. individual) will be infused following the thermal and ischemic tasks (before CPM procedures). This dose will be used to maintain adequate opioid blockade across the duration of pain-induction procedures.

Study Interventions

Both study treatment interventions will consist of 8 weekly, 1-1.5 hr individual sessions. For MT and SMT, the content of each session will be based on a standardized treatment manual. Manuals will contain detailed session by session information, instructions and scripts for therapists, and patient handouts.

Mindfulness Training (MT)

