6. STUDY PROCEDURES

6.1 Schedule of Evaluations (see table)

Session	Pre-Treatment			Intervention								Post		Follow-up				
	Baseline	Lab 1	Lab 2	1	2	3	4			5	6	7	8	9		3m	6m	
Informed Consent	X																	
Demographics (SR)	X													Lab 1	Lab 2			
AEI (SR)															X			
Bothersome Pain Item (SR)	X			X*	X*	X*	X*			X*	X*	X*	X*			X	X	
Desirability of Control/Health Locus of Control (SR)																X		
Evoked Pain Intensity and Unpleasantness (SR)		X	X											X	X			
FFMQ-15/MAIA (SR)	X			X*	X*	X*	X*			X*	X*	X*	X*			X	X	
Healthcare Utilization (SR)	X														X	X	X	
Concomitant Medication	X	X	X											X	X	X	X	
HOME Opioid Questionnaire (SR)	X																	
McGill Pain Questionnaire (SR)		X	X											X	X			
MPQ (back pain- past week) (SR)	X													X		X	X	
Oswestry Low Back Disability (SR)	X													X		X	X	
Pain Catastrophizing Scale (SR)	X			X*	X*	X*	X*			X*	X*	X*	X*			X	X	
Pain Self-Efficacy Questionnaire (SR)	X			X*	X*	X*	X*			X*	X*	X*	X*			X	X	
PROMIS Anger/Anxiety/Depression/Pain Interference & Intensity/Sleep/Physical Function/Instrumental Support/Emotional Support (SR)		X			X*	X*	X*	X*			X*	X*	X*	X*			X	X
Working Alliance Inventory/Scale to Assess Therapeutic Relationship- Patient Version						X+					X+							
Reaction to Treatment Questionnaire (CEM)			X			X+					X+							
Pain Detect Questionnaire (SR)	X																	
Pain Stages of Change Questionnaire (SR)	X			X*	X*	X*	X*			X*	X*	X*	X*			X	X	
Naloxone Side Effects (SR)		X	X												X	X		
Patient Engagement Checklist (completed by therapist)				X	X	X	X			X	X	X	X					
Spinal Stiffness (before and after session- done via Vertetrack)				X	X	X	X			X	X	X	X					

Height & Weight (measured by scale)	X															
Blood Pressure (measured by Dinamap)	X															
Blood Draw (collected by RN)		X	X											X	X	
Urine Test (Opioid and Pregnancy-if female)		X	X											X	X	
Quantitative Sensory Testing		X	X											X	X	
If applicable: COVID-19 Safety Precautions (temperature check, travel history, signs/symptoms questionnaire)	X	X	X	X	X	X	X			X	X	X	X	X	X	X

*Survey is done via phone call with research assistant and research assistant enters directly into REDCap or survey is entered directly into REDCap online by participant

+ Survey is done via pen and paper by participant and entered into REDCap by RAs (therapist-blinded)

SR = self-report. Will be directly entered into REDCap by participant

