6.2.1 Phone Screening Evaluation

Potential participants responding to ads, flyers, etc., will be contacted by phone after indicating their desire to be contacted (via e-mail or phone call). They will be asked whether they agree to provide basic medical information in order to determine their study eligibility. If responding positively, they will be asked whether they have daily pain of at least 3 months duration, which is of an average intensity of at least 4/10 (with 0 being “no pain” and 10 “the worst pain possible”), and presents substantial interference in performance of social, work, and everyday activities ($\geq 3/10$ on a 10-point scale). They will be asked whether: 1) their pain is musculoskeletal pain of the lower back and/or leg; 2) they are aged between 18 and 75 years; 3) can understand English well enough to complete questionnaires or to participate in therapy; 4) their pain is due to malignant conditions, rheumatoid arthritis, complex regional pain syndrome, or fibromyalgia syndrome; 5) they have had lumbar surgery within the past 6 months or have ever had spinal fusion surgery; 6) they are pregnant; 7) they have had liver disease such as hepatitis or cirrhosis; 8) they have osteoporosis; 9) they have any active suicidal ideation with intent; 10) they have opioid-dependency or use Kratom daily; 11) they can hold their breath for 15 seconds; 12) they have acute trauma to spine; 13) they have long term use of corticosteroids; 14) they have a spinal cord stimulator, IT pump, or a similar device; 15) they have signs of nerve root compression (i.e., positive straight-leg raise $<45^\circ$); 16) they meet criteria for past or present psychotic or bipolar disorders; 17) arthritis of the hand, carpal tunnel syndrome, or any neuropathic pain diagnoses affecting the upper limbs; and 18) they have a BMI of ≥ 40 . If they meet eligibility criteria, they will be invited to an in-person interview.

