- Baseline demographics, neuropathy (painDETECT questionnaire), medication and healthcare use, opioid use (HOME Opioid Questionnaire), bothersome pain, back pain (McGill Pain Questionnaire) and disability (Oswestry Low Back Disability), and attitudes on changing pain (Pain Stages of Change Questionnaire) will also be assessed.
- Pain catastrophizing will be assessed with the Pain Catastrophizing Scale.
- Mindfulness will be assessed with the Five Facets of Mindfulness Questionnaire (short form), and the Multidimensional Assessment of Interoceptive Awareness (short form).
- Self-efficacy will be assessed with the Pain Self-Efficacy Questionnaire.
- Height and weight will be measured using a scale.
- Blood pressure will be measured using a Dinamap blood pressure monitor.

Pre-Treatment Lab Sessions (Visits 2 & 3)

- A urine sample will be collected and tested for opioids (using a rapid single panel opioid screening test) and pregnancy (females only – using an analog pregnancy test).
- Baseline assessment of opioid function and conditioned pain modulation will be assessed via the Quantitative Sensory Testing (QST) procedures described below.
- To enable potential future assessment of treatment-related changes in relevant biomarkers, a 4mL sample of whole blood will be drawn from the cannula placed for drug administration into a tube with EDTA prior to beginning laboratory pain or drug administration procedures in both laboratory sessions. Within 10 minutes of collection, samples will be centrifuged for 10 minutes at 3500rpm and 4°C. Plasma will then be pipetted into microcentrifuge tubes (0.5mL aliquots) and stored at -80°C until assayed.
- McGill Pain Questionnaire administered during the QST procedures in several versions to capture pain in back before and after each procedure.
- Evoked pain intensity and unpleasantness and naloxone side effects will be assessed.
- Assessment of any adverse events.

Endogenous Opioid (EO) Function

As in our previous work (68-72), we will use a placebo-controlled opioid blockade procedure to assess treatment-induced changes in EO function. Naloxone is an opioid antagonist with a brief half-life (1.1 hours; 78). We will use a weight-adjusted dose of 0.11 mg/kg with a maximum dose of 8mg (8mg dose for a 160 lb. individual,

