A heat pain task using a Medoc TSAII NeuroSensory Analyzer (Medoc US., Minneapolis, MN) will then follow. This equipment will be used to assess heat pain threshold and tolerance using an ascending method of limits protocol as used in our prior work (68,71,72). The equipment to be used has a hardware temperature cutoff of 51°C in order to prevent tissue injury. Four trials each will be conducted for heat pain threshold and tolerance, with each trial conducted sequentially at 1 of 4 different non-overlapping sites on the non-dominant ventral forearm. An interval of 30 secs between successive stimuli will be employed. For threshold trials, the probe will start at an adaptation temp of 32°C, with the temp increasing at a ramp rate of 0.5°C/sec until the subject indicates that the stimulus has begun to feel "painful." For tolerance trials, the probe will start at an adaptation temperature of 40°C, with the temperature increasing at a ramp rate of 0.5°C/sec until the subject indicates maximum tolerance has been reached. Means of the 4 thermal pain threshold and tolerance trials will be derived for use in analyses. Immediately upon completion of the final heat pain tolerance trial, subjects will be asked to rate the overall pain experienced during this

trial using the MPQ. EO function will be operationalized as in our past work as changes in evoked pain responses between the placebo and naloxone conditions (68,71,72), with blockade effects on the visual analog scale (VAS) pain intensity measure of the MPQ considered primary.

Conditioned Pain Modulation (CPM)

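### Abstinence from Kratom before each laboratory session is said to be confirmed by urine screen, but the protocol specifies no urine test for Kratom

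*Protocol*

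**What the plan says.** **The eligibility rule.** Section 4.1 requires participants to be "not using opioid analgesics or Kratom on a daily basis or within 3 days of each laboratory session (confirmed via urine drug screen"). The précis and the introduction to section 4 carry the same rule. Two substances are named, and a single parenthesis claims confirmation for both.

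**The test.** At the pre-treatment laboratory visits (section 6.2.2) urine is "tested for opioids (using a rapid single panel opioid screening test"), with a pregnancy test for women. Section 6.2.4 specifies the same tests at the post-treatment laboratory visits. The row in the section 6.1 schedule reads "Urine Test (Opioid and Pregnancy-if female").

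**The rule as restated for naloxone.** Section 5.1 and the endogenous opioid (EO) text of section 6.2.2 exclude "participants using opioid analgesics on a daily basis or within 3 days of each laboratory session (confirmed via urine drug screen"), and also anyone with withdrawal symptoms at the first naloxone administration. Kratom is not mentioned there.

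**Other checks that name Kratom.** The exclusion in section 4.2 is "opioid-dependency or daily use of Kratom". The phone screen in section 6.2.1 asks whether "they have opioid-dependency or use Kratom daily".

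**The endpoint.** Section 6.2.2 states that "EO function will be operationalized as in our past work as changes in evoked pain responses between the placebo and naloxone conditions". Section 9.5.1 makes its pre- to post-treatment change the primary mechanism outcome.

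**The concern.** The criterion lists Kratom separately from opioid analgesics, so a reader cannot take it for granted that an opioid panel covers both. The protocol never says that it does. For Kratom, the three-day condition is stated as objectively verified while no method of verification is given.

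Two things are at stake. The first is the truth of the eligibility statement: a report saying that Kratom abstinence was confirmed by urine would go beyond what was done. The second is the measurement. The three-day rule governs the sessions in which pain under naloxone is compared with pain under placebo, and the protocol itself places Kratom beside opioids in that rule. On that logic, use before some sessions and not others could be scored as a change in EO function.

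**Working it through.** **1. Text against text.**

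| Place in protocol | Substances covered | Time covered | Means of checking |
|---|---|---|---|
| Précis; section 4 introduction; 4.1 | Opioid analgesics and Kratom | Daily, or within 3 days of each laboratory session | Urine drug screen |
| 5.1; 6.2.2 (EO function) | Opioid analgesics only | Daily, or within 3 days of each laboratory session | Urine drug screen |
| 6.1; 6.2.2; 6.2.4 | Opioids (plus pregnancy) | Four laboratory visits | One opioid panel |
| 4.2, criterion 10 | Opioid dependency; Kratom | Kratom: daily use | Not stated |
| 6.2.1, item 10 | Opioid dependency; Kratom | Kratom: daily use | Self-report |

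For opioids, rule, time window and test line up. For Kratom, the first row claims a urine confirmation that no other row supplies, and the naloxone row drops the substance. The Concomitant Medication entry in the schedule falls at all four laboratory visits, but nothing says that it asks about Kratom or the date of last use.

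**2. The plan's own figures.** Section 9.2 gives 0.851 for the Aim 1 equivalence test: 120 per arm, SD 7.5, limits ±3.0, true difference 0, alpha 0.05 for each one-sided test. The exact t-based calculation with 238 degrees of freedom gives 0.8515. Enrolment also reproduces: 240 / (1 − 0.16) = 285.7, rounded up to 286. The point disputes neither figure.

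**3. What contamination could do, by assumption only.** The protocol gives no frequency of Kratom use and no size of effect on EO change. Suppose a share f of participants has an EO change shifted by k points in one direction. Both f and k are assumptions without a source.

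*Same share in both arms.* SD = √(7.5² + f(1 − f)k²), and the true difference stays 0.

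- f = 1%, k = 10: SD = √(56.25 + 0.99) = 7.57, power 0.844
- f = 5%, k = 10: SD = √(56.25 + 4.75) = 7.81, power 0.814
- f = 5%, k = 20: SD = √(56.25 + 19.00) = 8.67, power 0.695

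*One arm only.* Here f is the share of that arm, the shift in the arm difference is f × k, and the SD is √((7.5² + SD²)/2), with SD from the formula above.

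- f = 5%, k = 10: shift 0.5 points against the limit of 3.0, power 0.780
- f = 10%, k = 20: shift 2.0 points, power 0.225

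If 1–5% of all 240 completers were affected and all were in one arm of 120, that would be 2–10% of the arm. With k from 10 to 20, the shift would run from 0.02 × 10 = 0.2 to 0.10 × 20 = 2.0 points. A shift of 10 to 20 points is 1.3 to 2.7 times the planning SD, so the upper end is an extreme case.

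**The case against.** The case against making much of this has four parts.

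- **The test's performance is not documented.** A reader might infer that the panel cannot detect Kratom. The protocol lists neither the panel's analytes nor its cross-reactivity, so that inference is unsupported. What stands is that no test for Kratom is specified and no coverage is claimed for the panel.
- **There are other safeguards.** Withdrawal symptoms at the first naloxone dose exclude a participant whatever the substance. Screening covers substance use disorder items and current and over-the-counter medicines, and Concomitant Medication is recorded at each laboratory visit. These make unnoticed use less likely. None is a urine confirmation, and none is said to cover Kratom within the three-day window.
- **The rule in 4.1 still applies.** The shorter wording in 5.1 and 6.2.2 does not cancel the Kratom condition, which refers to every laboratory session. That is fair, but staff working from the naloxone text would apply a narrower check.
- **The effect is hypothetical.** A reader might infer that the primary contrast is biased. Nothing in the protocol shows that Kratom was used or how far it would move EO change, and no reason is given to expect different use by arm. Balanced use mainly adds noise, and at 1% and 10 points the loss of power is under 0.01.

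These objections limit the consequence. They leave the textual mismatch untouched.

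**Conclusion.** The point holds as a mismatch within the protocol: a urine confirmation is claimed for two substances and a urine test is specified for one. That conclusion rests on the text alone and on no assumption about how often Kratom is used.

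The consequence for the primary mechanism outcome is possible, not shown, and cannot be sized from the protocol. The illustrative range runs from almost nothing to a material loss of power, and its upper end needs frequent use, a large effect and confinement to one arm.

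A reader might also infer that the naloxone text is wrong to leave Kratom out. The protocol does not settle that. It states the rule in two ways, and which eligibility rule applies before naloxone is for the sponsor to decide.

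**What to change.** The sponsor should reconcile three sets of text: the précis, the section 4 introduction and 4.1; the naloxone text in 5.1 and 6.2.2; and the test specifications in 6.1, 6.2.2 and 6.2.4. Two routes make the eligibility statement true:

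- Limit the claim of urine confirmation to opioids and state that recent Kratom use is ascertained by self-report. Record the date of last use on the Concomitant Medication form at each of the four laboratory visits, so that affected sessions can be identified in the EO analysis.
- Or keep the claim and name a urine test that covers Kratom.

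The first route costs a wording change and one dated item on a record already taken at those visits. Its downside is that Kratom status then rests on self-report. The second needs a different or additional test. How flagged sessions are treated in the analysis can be left to the statistical analysis plan.
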